**Table 3. Microbiological Outcome**

Category	Criteria
Eradication	Blood cultures negative for SA for 2 consecutive days.
Presumed eradication	Follow-up blood cultures were not done (or were technically uninterpretable) and the subject has responded clinically, as defined in Table 2 of protocol .
Persistence	Follow-up blood cultures do not meet the criteria for eradication and are positive for SA either daily or every other day.
Presumed persistence	Follow-up blood cultures were not done (or were technically uninterpretable) and the subject has not responded clinically, as defined in Table 2 of protocol .
Recurrence	A positive blood culture for SAB at any time after documented eradication or presumed eradication.

In [Table 3](#), “the subject has responded clinically” indicates that the subject experiences clinical improvement or response per investigator’s assessment at EOT for study drug. Any 2 consecutive assessments with blood cultures negative for SA is assigned as Eradication programmatically, no matter if these 2 assessments are consecutive days or consecutive visits.

Time to first resolution of any signs/symptoms related to focal site of SA infection (e.g., joint pain; redness; swelling; weight-bearing, back pain; weight-bearing, skin redness; drainage) from randomization on Day 1 will be analyzed. If all signs/symptoms are absent, the subjects will be considered achieving the resolution of signs/symptoms related to focal site of SA infection. If any signs/symptoms are present during the study assessments, the subjects will be censored at the date of latest assessment of signs/symptoms assessments for focal site of SA infection.

Time-to-event (days) = Censoring date/date of first resolution assessment – date of first dose of study drug + 1

The Kaplan-Meier method will be used to estimate the 25%, median and 75% times. The hazard ratio, 95% confidence interval (CI) of hazard ratio, and p-value from Cox regression model will be provided to compare AP-SA02 and placebo. Cox regression will include treatment (AP-SA02 and placebo) as factor. All assessments from scheduled and unscheduled visits will be included in the time-to-event analysis.

The Kaplan-Meier plot of time to first resolution of any signs/symptoms related to focal site of SA infection will be provided.

Late composite efficacy will be assessed programmatically based on the blood cultures tested by local microbiology laboratories per the definition in [section 2.3.2](#) at EOS. Proportion of subjects who experience late composite efficacy will be provided. Chi-square test p-value will be provided for the counts of subjects who experience late composite efficacy to compare AP-SA02 and placebo.

Microbiological failure or relapse will be assessed programmatically based on the blood cultures tested by local microbiology laboratories per the definition in section 2.3.2. Proportion of subjects who experience microbiological failure or relapse at TOC for study drug (Day 12), TOC for BAT (7 days [ $\pm 1$  day] after the end of BAT) and EOS (28 days after the end of BAT) will be provided.

If subjects have microbiological failure or relapse at TOC for study drug (Day 12) and negative blood cultures after Day 12, then subjects will not be included as microbiological failure or relapse at TOC for BAT (7 days [ $\pm 1$  day] after the end of BAT) or EOS (28 days after the end of BAT). If subjects have microbiological failure or relapse at TOC for BAT (7 days [ $\pm 1$  day] after the end of BAT) and negative blood cultures after TOC for BAT, then subjects will not be included as microbiological failure or relapse at EOS (28 days after the end of BAT). Chi-square test p-value will be provided for the counts of subjects who experience microbiological failure or relapse to compare AP-SA02 and placebo.

Time to death will be analyzed. Subject alive will be censored at the last date to be known alive.

$$\text{Time to death (days)} = \text{Censoring date/death date} - \text{date of first dose of study drug} + 1$$

The Kaplan-Meier method will be used to estimate the 25%, median and 75% times. The hazard ratio, 95% confidence interval (CI) of hazard ratio, and p-value from Cox regression model will be provided to compare AP-SA02 and placebo. Cox regression will include treatment (AP-SA02 and placebo) as factor.

Time to hospital discharge (and time to hospital discharge readiness) will analyzed. The subjects who will be in the hospital during the study will be censored at the date of last visit.

- Time to hospital discharge (days) = Censoring date/first hospital discharge date – date of first dose of study drug + 1
- Time to hospital discharge readiness (days) = Censoring date/first hospital discharge readiness date – date of first dose of study drug + 1

The Kaplan-Meier method will be used to estimate the 25%, median and 75% times. The hazard ratio, 95% confidence interval (CI) of hazard ratio, and p-value from Cox regression model will be provided to compare AP-SA02 and placebo. Cox regression will include treatment (AP-SA02 and placebo) as factor.

The Kaplan-Meier plot of time to hospital discharge (and time to hospital discharge readiness) will be provided.

Need for ICU stay will be summarized with counts and percentages of subjects. Chi-square test p-value will be provided for the counts of subjects who need ICU stay to compare AP-SA02 and placebo.

Duration of ICU stay during the study period from the Day 1 will be summarized with descriptive statistics for subjects who need for ICU stay.

The duration of ICU stay can be calculated as sum of each ICU stay from date of admission to date of discharge when the type of hospitalization is “ICU” in eCRF.

A t-test p-value will be provided for duration of ICU stay to compare AP-SA02 and placebo.

Need for endotracheal mechanical ventilation will be summarized with counts, and percentages of subjects. Chi-square test p-value will be provided for the counts of subjects who need endotracheal mechanical ventilation to compare AP-SA02 and placebo.

The type of oxygen delivery methods will be collected in eCRF, and the endotracheal mechanical ventilation will include types “*mechanical ventilation via tracheotomy*” and “*endotracheal tube*” in eCRF.

Duration of endotracheal mechanical ventilation will be summarized with descriptive statistics for subjects who need for endotracheal mechanical ventilation during the study.

Need for noninvasive pressure ventilation (e.g., continuous positive airway pressure, bilevel positive airway pressure) will be summarized with counts, and percentages of subjects. Chi-square test p-value will be provided for the counts of subjects who need noninvasive pressure ventilation to compare AP-SA02 and placebo. Noninvasive pressure ventilation includes oxygen delivery methods, i.e., nasal cannula, high-flow nasal cannula, nonrebreather face mask, CPAP mask, BiPAP mask, BiPAP hood and other which are collected in eCRF.

Duration of noninvasive pressure ventilation will be summarized with descriptive statistics for subjects who need for noninvasive pressure ventilation during the study.

The analysis of SA isolate sensitivity to AP-SA02, SA isolate susceptibilities to anti-staphylococcal antibiotics, and SA isolate susceptibility to BAT will be reported by the Sponsor separately.

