7.8 Microbiological Outcome

Microbiological response will be determined programmatically as 1 of the following outcomes based on the results of blood cultures and/or urine cultures at EOT for study drug (Day 5), TOC for study drug (Day 12), TOC for BAT, and EOS. A microbiological favorable assessment will include eradication and presumed eradications, as detailed in [Table 5](#).

Table 5. Microbiological Outcome

Category	Criteria
Eradication	Blood cultures negative for SA for 2 consecutive days.
Presumed eradication	Follow-up blood cultures were not done (or were technically uninterpretable) and the subject has responded clinically, as defined in Table 2 .
Persistence	Follow-up blood cultures do not meet the criteria for eradication and are positive for SA either daily or every other day.
Presumed persistence	Follow-up blood cultures were not done (or were technically uninterpretable) and the subject has not responded clinically, as defined in Table 2 .
Recurrence	A positive blood culture for SAB at any time after documented eradication or presumed eradication.
SA = Staphylococcus aureus ; SAB = Staphylococcus aureus bacteremia.	

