## 3.6 Pharmacodynamic Assessment

Pharmacodynamic assessment will be conducted for ITT population, Per Protocol MITT population, Phage Persistence and Clearance population, and Phage-Sensitivity ITT population (if needed):

- Efficacy analysis performed using ITT population and Phase-Sensitivity ITT population (if needed) will be summarized by pooled treatment versus pooled placebo for Phase 1b and Phase 2a:
  - Phase 1b (uncomplicated SAB) vs Phase 1b placebo

- Phase 2a (complicated SAB) vs Phase 2a placebo.
- Efficacy analysis performed using Per Protocol MITT population will be summarized by pooled treatment versus pooled placebo for Phase 2a:
  - Phase 2a vs Phase 2a placebo.
- Efficacy analysis performed using Phage Persistence and Clearance population will be summarized by following:
  - Combination of Phase 1b (excluding cohort 1) and Phase 2a Persistence vs Combination of Phase 1b (excluding cohort 1) and Phase 2a Clearance vs Combination of Phase 1b placebo (excluding cohort 1) and Phase 2a placebo
  - Phase 2a Persistence vs Phase 2a Clearance vs Phase 2a placebo

Combination of Phase 1b placebo (excluding cohort 1) and Phase 2a placebo includes Phase 1b placebo (excluding cohort 1) and Phase 2a placebo in ITT population. Phase 2a placebo includes Phase 2a placebo in ITT population.

Phage Persistence and Phage Clearance Population and Phage-Sensitivity ITT population (if needed) will be reported by the Sponsor separately. Subject lists for Phage Persistence and Phage Clearance Population and Phage-Sensitivity ITT population (if needed) will be provided by Sponsor for analysis.

Time to initial resolution of SAB will be analyzed using the Kaplan-Meier method, and the resolution will be defined as “2 consecutive days with negative SA blood cultures” based on blood cultures tested by the local microbiology laboratories. Blood cultures collected at Day 1 prior to first dose of study drug will be considered for initial resolution of SAB.

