If Day 12 blood culture is positive, the subject will not be considered have initial resolution of SAB although there may be 2 or more consecutive negative blood cultures before Day 12. If EOS or BAT blood culture is positive, the subject will be considered as initial resolution of SAB when there are 2 or more consecutive negative blood cultures before EOS or BAT, and the initial resolution date and time will be the first date and time with 2 consecutive negative blood cultures. The subjects who do not experience the resolution will be censored at the last collection date and time of blood culture.

- Time to initial resolution of SAB (days) = (Censoring date and time/first date and time of 2 consecutive days with negative SA blood culture – date and time of first dose of study drug) /3600/24

The Kaplan-Meier method will be used to estimate the 25%, median and 75% times. The hazard ratio, 95% confidence interval (CI) of hazard ratio, and p-value from Cox regression model will be provided to compare AP-SA02 and placebo. Cox regression will include treatment (AP-SA02 and placebo) as factor.

The Kaplan-Meier plot of time to initial resolution of SAB will be provided.

Time to resolution of any signs and/or symptoms of bacteremia present at Screening will be analyzed using the Kaplan-Meier method as other time-to-event endpoints.

- Time to resolution of signs/symptoms of bacteremia (days) = Censoring date/date of first resolution of any signs/symptoms of bacteremia - date of first dose of study drug + 1

The Kaplan-Meier method will be used to estimate the 25%, median and 75% times. The hazard ratio, 95% confidence interval (CI) of hazard ratio, and p-value from Cox regression model will be provided to compare AP-SA02 and placebo. Cox regression will include treatment (AP-SA02 and placebo) as factor.

The Kaplan-Meier plot of time to resolution of any signs and/or symptoms of bacteremia present at Screening will be provided.

The signs and symptoms of SAB will be determined programmatically based on the following:

- Documented temperature  $\geq 38.0^{\circ}\text{C}$  ( $100.4^{\circ}\text{F}$ ) or  $\leq 36.0^{\circ}\text{C}$  ( $96.8^{\circ}\text{F}$ ) measured orally,  $\geq 38.5^{\circ}\text{C}$  ( $101.3^{\circ}\text{F}$ ) or  $\leq 36.5^{\circ}\text{C}$  ( $97.7^{\circ}\text{F}$ ) measured tympanically, or  $\geq 39^{\circ}\text{C}$  ( $102.2^{\circ}\text{F}$ ) or  $\leq 37^{\circ}\text{C}$  ( $98.6^{\circ}\text{F}$ ) measured rectally;

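### Clearance of bacteremia is defined in two ways, so a subject can be classed as eradicated in one endpoint and censored as never resolved in another

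*SAP*

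**What the plan says.** Microbiological outcome: protocol 7.8 (Table 5) defines eradication as "Blood cultures negative for SA for 2 consecutive days", and SAP Table 3 repeats this. The note beneath SAP Table 3 then gives the programming rule: "Any 2 consecutive assessments with blood cultures negative for SA is assigned as Eradication programmatically", and adds "no matter if these 2 assessments are consecutive days or consecutive visits".

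Time to initial resolution of SAB (SAP 3.6): resolution is "2 consecutive days with negative SA blood cultures". The formula takes the event time as the "first date and time of 2 consecutive days with negative SA blood culture". In handling late positive cultures, the same section says "the initial resolution date and time will be the first date and time with 2 consecutive negative blood cultures". On censoring: "The subjects who do not experience the resolution will be censored at the last collection date and time of blood culture".

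Relapse (SAP 2.3.2, protocol 7.2): the third criterion counts 72 hours from clearance, which is again two consecutive negative days.

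Schedule (protocol 7.7, Appendix A): cultures are mandatory on Days 1, 5, 7 and 12, at TOC for BAT and at EOS. Days 2, 3, 4 and 6 are drawn only until two consecutive negative days are reached, or if clinically indicated. The grid lists no visit between Day 7 and Day 12.

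SAP Section 6 lists six changes from the protocol. The looser eradication rule is not one of them.

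**The concern.** Eradication, relapse and time to resolution describe the same biological event and, per the SAP, come from the same local-laboratory cultures. If they are programmed from different sentences, the same subject can be a success in the eradication table and a permanent non-event on the Kaplan-Meier curve. The relapse criterion would also have no clearance date to count from for that subject.

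SAP 3.6 does not settle its own rule either. A programmer following its definition and formula gets one set of events and dates; one following its wording about consecutive cultures gets another. Both results carry p-values (chi-square for eradication, Cox for resolution) in about 42 Phase 2a subjects randomized 2:1, so a few reclassified subjects would be visible.

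**Working it through.** **1. One subject, traced through the rules.** All scheduled cultures are taken: positive on Day 6; negative on Day 7, Day 12, at TOC for BAT and at EOS.

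- Note under SAP Table 3: Days 7 and 12 are consecutive assessments, so Eradication from Day 12.
- SAP 3.6 definition and formula: no two negative cultures fall on consecutive days, so there is no event and the subject is censored at EOS (Days 39 to 81 in the grid).
- SAP 3.6 wording on consecutive cultures: event dated to Day 7.
- Relapse, third criterion: clearance never occurs, so the 72-hour clock never starts.

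**2. All possible patterns.** Both rules were applied to every positive/negative series the schedule allows, with TOC for BAT placed at Day 35 and EOS at Day 56 (assumptions; other permitted days give the same classification). There are 592 distinct patterns. In 128, eradication is met but two consecutive negative days never occur; 13 of these are negative on every culture from Day 7 on. A further 160 have two consecutive negative days but lose resolution through a separate, explicit rule: "If Day 12 blood culture is positive, the subject will not be considered have initial resolution of SAB". These are counts of logical patterns, not expected frequencies in patients.

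**3. How often, under assumptions.** The documents give no clearance rate. Assume each subject still bacteremic clears with probability h per day and stays clear, that optional cultures are missed with probability m, that none are drawn on Days 8 to 11, and that follow-up stops at Day 12. With m = 0, the discordant subjects are those first negative exactly on Day 7, a share of h(1−h)^6:

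- h = 0.2: 0.2 × 0.8^6 = 0.2 × 0.262 = 5.2%
- h = 0.3: 0.3 × 0.7^6 = 0.3 × 0.118 = 3.5%
- h = 0.4: 0.4 × 0.6^6 = 0.4 × 0.047 = 1.9%

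Simulation gives, for m = 10% and 20%: 7.0% and 9.6% (h = 0.2); 5.0% and 7.5% (h = 0.3); 3.0% and 5.2% (h = 0.4). At h = 0.6 the range is 0.2% (m = 0) to 2.1% (m = 20%).

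Carried on to EOS with m = 0, anyone first negative on Day 7 or later can never meet the two-day rule on scheduled cultures alone. That share is (1−h)^6: 26%, 12% and 5% for h = 0.2, 0.3 and 0.4.

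If daily cultures instead continue to Day 11 until two consecutive negative days are obtained, the share first clear by Day 7 but never resolved falls to 0.0–0.1% for every h and m tested.

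**4. Effect on the hazard ratio.** Cox models were fitted to large simulated samples with h = 0.4 on active and 0.2 on placebo and no cultures on Days 8 to 11. Hazard ratio for resolution, two-day rule versus any-two-assessments rule, in two separate runs:

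- m = 0: 2.24 vs 2.21; 2.20 vs 2.18
- m = 10%: 2.19 vs 2.22; 2.23 vs 2.28
- m = 20%: 2.12 vs 2.23; 2.14 vs 2.26

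In the first run (90,000 subjects, 2:1) the standard error of the log hazard ratio was about 0.008. With no missed cultures the two-day rule gives a marginally larger ratio; with missed cultures it gives a smaller one, because missed days also delay or remove events on active.

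**The case against.** The best defence is protocol 7.7 itself. It asks for cultures until two consecutive negative days are obtained, so a subject first negative on Day 7 should be cultured again on Day 8. If sites do that, the discordance almost disappears for subjects clear by Day 7. This stands as a limit on size. It does not remove the conflict, because the grid schedules nothing between Days 7 and 12 and actual practice is unknown.

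The looser rule also has a reason: outcome is classified at TOC for BAT and EOS, where no consecutive-day cultures are scheduled. That explains the note, but not why resolution and relapse keep a different rule or why Section 6 is silent.

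If SAP 3.6 were programmed throughout as two consecutive cultures, eradication and resolution would agree on this point. But its definition and formula say days, so the text does not select that reading.

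Three stronger readings are tempting and not supported:

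- *That the strict rule exaggerates a drug benefit by keeping late placebo clearers as non-events.* Discordance can be unequal (7.0% on placebo versus 3.0% on active at m = 10%), but the fitted hazard ratios move little, and downward when cultures are missed.
- *That subjects negative on Days 5 and 7 with Day 6 undrawn arise from the schedule.* If Day 5 is the first negative, Appendix A footnote r makes Day 6 necessary, so this case needs a missed culture.
- *That the two Day 1 sets, drawn 30 minutes apart, already count as resolution.* This is possible only on the loosest wording, and the definition and formula both speak against it.

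**Conclusion.** The inconsistency is real and rests on the text alone: two consecutive days in SAP Table 3, protocol Table 5, the relapse endpoint and the SAP 3.6 definition and formula; any two consecutive assessments in the note under Table 3; two consecutive cultures elsewhere in SAP 3.6. Followed literally on the scheduled cultures, it classes the same subject as eradicated and never resolved.

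Its size is not established. The 2% to 10% range by Day 12 depends on assumed clearance probabilities and on no cultures on Days 8 to 11. Even h = 0.2 is a strong assumption, since it leaves 0.8^7 = 21% still bacteremic after Day 7. A reader might turn the range into a count of Phase 2a subjects, but the documents do not support an expected number. The effect on the hazard ratio was small and of no fixed direction in the scenario examined, so no claim of exaggerated benefit should be made.

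SAP 3.1.4 plans no formal testing, which lowers the stakes, though p-values are still reported. This should be corrected before database lock as a matter of definition. The Day 12 override is a separate, stated choice and is not part of this point.

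**What to change.** Program one clearance rule for eradication and recurrence (SAP Table 3), microbiological relapse (SAP 2.3.2) and time to initial resolution (SAP 3.6): two consecutive negative cultures on different study days, with no positive between them, dated to the first of the two. Count the two Day 1 sets as one assessment that is negative only if both are negative. Use the same words in all three places, list the change in SAP Section 6, and report the strict consecutive-day rule as a sensitivity analysis.

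The cost is SAP wording and programming; no new data are needed. The downside is slightly coarser clearance dates when the two cultures are several days apart.

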7.2 Phase 2a Endpoints

The Phase 2a endpoints are the following:

- Time to reach a NEWS2 score ≤ 2 maintained for at least 24 hours or hospital discharge (whichever comes first) for subjects on active drug versus placebo in the Microbiological Intent-to-Treat (MITT) Population;
- Clinical Improvement or response at TOC for study drug (Day 12) in the MITT Population;
- Proportion of subjects reaching a NEWS2 score ≤ 2 maintained for at least 24 hours or hospital discharge (whichever comes first) for subjects on active drug versus placebo at TOC for study drug (Day 12) in the MITT Population;
- Microbiological outcome at EOT for study drug (Day 5);
- Clinical Improvement or response at TOC for BAT (7 days [± 1 day] after the end of BAT);
- Clinical Improvement or response at EOS (28 days after the end of BAT);
- Time to death;
- NEWS2 score while hospitalized by study day;
- Late composite efficacy, as defined by the following:
 - Survival at EOS (Days 39 to 81); and
 - No evidence of microbiological failure, as defined by either of the following:
 - Blood cultures that remain positive for SA ≥ 7 days from randomization; or
 - Isolation of SA from the blood or another sterile site (eg, joint fluid, tissue) > 14 days from randomization.

- Microbiological failure or relapse by any of the following:
 - Blood cultures that remain positive for SA ≥ 7 days from randomization;
 - Isolation of SA from the blood or another sterile site (eg, joint fluid, tissue) >14 days from randomization; or
 - Blood culture positive for SA >72 hours after the first blood cultures showing CL of SAB (defined as 2 consecutive days with negative SA blood cultures).
- Time to resolution of SAB;
- Time to hospital discharge (and time to hospital discharge readiness);
- Need for and duration of intensive care unit stay;
- Need for and duration of endotracheal mechanical ventilation;
- Need for and duration of noninvasive pressure ventilation (eg, Continuous Positive Airway Pressure, Bilevel Positive Airway Pressure);
- PK of AP-SA02 with IV administration;
- Relationship between AP-SA02 exposures and safety and efficacy endpoints;
- Immunogenicity of AP-SA02 at EOS;
- Time to resolution of any signs and/or symptoms of bacteremia present at Screening;
- Time to resolution of any signs/symptoms related to focal site of SA infection (eg, joint pain; redness; swelling; weight-bearing, back pain; weight-bearing, skin redness; drainage) from randomization on Day 1;

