### 2.3.2 Phase 2a Endpoints

The Phase 2a endpoints are the following:

- Time to reach a National Early Warning Score 2 (NEWS2) score  $\leq 2$  maintained for at least 24 hours or hospital discharge (whichever comes first) for subjects on active drug versus placebo
- Clinical Improvement or response at TOC for study drug (Day 12)
- Proportion of subjects reaching a NEWS2 score  $\leq 2$  maintained for at least 24 hours or hospital discharge (whichever comes first) for subjects on active drug versus placebo at TOC for study drug (Day 12)
- Microbiological outcome at EOT for study drug (Day 5)
- Clinical Improvement or response at TOC for BAT (7 days [ $\pm 1$  day] after the end of BAT)
- Clinical Improvement or response at EOS (28 days after the end of BAT)
- Time to death
- NEWS2 score while hospitalized by study day
- Late composite efficacy, as defined by the following:
  - Survival at EOS (Days 39 to 81); and
  - No evidence of microbiological failure, as defined by either of the following:
    - Blood cultures that remain positive for SA  $\geq 7$  days from randomization; or
    - Isolation of SA from the blood or another sterile site (e.g., joint fluid, tissue)  $> 14$  days from randomization.
- Microbiological failure or relapse by any of the following:
  - Blood cultures that remain positive for SA  $\geq 7$  days from randomization;
  - Isolation of SA from the blood or another sterile site (e.g., joint fluid, tissue)  $> 14$  days from randomization; or
  - Blood culture positive for SA  $> 72$  hours after the first blood cultures showing clearance of SAB (defined as 2 consecutive days with negative SA blood cultures).

- Time to initial resolution of SAB
- Time to hospital discharge (and time to hospital discharge readiness)
- Need for and duration of intensive care unit (ICU) stay
- Need for and duration of endotracheal mechanical ventilation
- Need for and duration of noninvasive pressure ventilation (e.g., Continuous Positive Airway Pressure, Bilevel Positive Airway Pressure)
- PK of AP-SA02 with IV administration
- Relationship between AP-SA02 exposures and safety and efficacy endpoints
- Immunogenicity of AP-SA02 at EOS
- Time to resolution of any signs and/or symptoms of bacteremia present at Screening
- Time to resolution of any signs/symptoms related to focal site of SA infection (e.g., joint pain; redness; swelling; weight-bearing, back pain; weight-bearing, skin redness; drainage) from randomization on Day 1

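### Microbiological failure or relapse is derived from cultures alone, so a subject who never clears and dies early is not counted as a failure

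*SAP*

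**What the plan says.** Protocol 7.2 and SAP 2.3.2 list "Microbiological failure or relapse by any of the following" and then give three limbs:

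1. Persistence: "Blood cultures that remain positive for SA" at 7 days or more from randomization.
2. Late isolation: "Isolation of SA from the blood or another sterile site (e.g., joint fluid, tissue") more than 14 days from randomization.
3. Relapse: a positive blood culture more than 72 hours after the first cultures showing clearance, which is "defined as 2 consecutive days with negative SA blood cultures".

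SAP 3.4.1 gives the derivation: "Microbiological failure or relapse will be assessed programmatically based on the blood cultures tested by local microbiology laboratories per the definition in section 2.3.2". The result to be reported is the "Proportion of subjects who experience microbiological failure or relapse at TOC for study drug (Day 12), TOC for BAT" and at EOS. The comparison follows: "Chi-square test p-value will be provided for the counts of subjects who experience microbiological failure or relapse to compare AP-SA02 and placebo".

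SAP 3.4.1 says when later negative cultures remove a subject from the failure count at a later visit. It does not say what happens when a subject dies. SAP 3.1.3 promises only in general terms that denominators will be defined, and none is given for this endpoint. SAP 3.1.5 covers incomplete dates for adverse events and medications, not missing efficacy outcomes.

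Neighbouring endpoints do deal with death or missing cultures. Protocol Table 2 makes death from any cause a non-response, and late composite efficacy requires survival to EOS. SAP Table 3 has a presumed-persistence category: "Follow-up blood cultures were not done (or were technically uninterpretable) and the subject has not responded clinically".

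**The concern.** An endpoint that can be met only by a culture taken at or after a given time cannot be met by someone who dies first. If the subject was still bacteremic, the worst microbiological course the trial can record adds nothing to the failure count. The arm with more of these deaths then shows a lower failure proportion than it should. A drug that prevents early bacteremic death would lose some of its apparent benefit here, and an arm with an excess of such deaths would look better than it is. The trial is small, so one or two subjects can visibly move the proportions and the p-value beside them.

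**Working it through.** **Can an early bacteremic death meet any limb?** Take a subject who never has two consecutive negative days and dies on Day 4.

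- Limb 1: no culture exists at 7 days or later. Not met.
- Limb 2: no isolate exists after 14 days. Not met.
- Limb 3: there was no clearance to relapse from. Not met.

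The derivation has no survival input, so the subject is not a failure at any of the three visits.

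**How wide is the gap?** Randomization is on Day 1 (protocol Appendix A), so the Day 7 culture falls 7 − 1 = 6 days after it. Read strictly, the first scheduled culture that can satisfy limb 1 is Day 12. Protocol 7.7 asks for cultures until two negative days are obtained, so a clinically driven culture between Day 8 and Day 11 could also qualify. A subject who clears and is positive again more than 72 hours later is captured by limb 3, even before death in the first week. The gap is therefore mainly for subjects who never clear. A subject who clears, turns positive again within 72 hours and then dies is also missed.

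**Size per death.** The documents state no rate or power for this endpoint, so there is no planned figure to reproduce. SAP 2.2.4 plans at least 38 MITT subjects at 2:1. 38 × 2/3 = 25.3, taken as 25 active and 13 placebo. One death kept as a non-failure instead of a failure changes the rate by 1/25 = 4.0 points on active or 1/13 = 7.7 points on placebo.

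**Effect of the denominator.** Let d be the proportion dying before clearance and f the failure proportion among the rest.

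- Deaths kept as non-failures: (1 − d)f
- Deaths dropped: f
- Deaths counted as failures: d + (1 − d)f

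Against the last line, keeping deaths understates an arm's rate by d, and dropping them understates it by d(1 − f). Both errors have the same direction and differ in size.

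The values of d and f below are assumptions. The last three columns are placebo minus active, in points.

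| d placebo / active | f placebo / active | Kept | Dropped | Counted |
|---|---|---|---|---|
| 10% / 5% | 20% / 10% | 18.0 − 9.5 = 8.5 | 10.0 | 28.0 − 14.5 = 13.5 |
| 15% / 5% | 20% / 10% | 17.0 − 9.5 = 7.5 | 10.0 | 32.0 − 14.5 = 17.5 |
| 5% / 15% | 20% / 20% | 19.0 − 17.0 = 2.0 | 0.0 | 24.0 − 32.0 = −8.0 |

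**Sensitivity of the p-value.** Assume 5/25 active and 3/13 placebo subjects are either culture failures or early bacteremic deaths. With deaths counted as failures the result is 20.0% against 23.1% however the events split (uncorrected chi-square p = 0.83). The rows below give the result with deaths kept as non-failures, and the rates if they are dropped.

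| Events that are deaths | Kept | p (kept) | Dropped |
|---|---|---|---|
| 2 of the 5 active | 12.0% vs 23.1% | 0.37 | 13.0% vs 23.1% |
| 3 of the 5 active | 8.0% vs 23.1% | 0.19 | 9.1% vs 23.1% |
| 5 of the 5 active | 0% vs 23.1% | 0.012 | 0% vs 23.1% |
| 2 of the 3 placebo | 20.0% vs 7.7% | 0.32 | 20.0% vs 9.1% |

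**The case against.** The strongest reply is that the death is visible elsewhere, and this stands. Microbiological outcome under SAP Table 3 is analysed at Day 5, Day 7 and the same three visits with its own chi-square test. On a natural reading it puts this subject in an unfavourable category. Clinical response, late composite efficacy and time to death also register the death. No formal testing is planned, the endpoint is one of a long unranked list, and the sample size rests on clinical response instead. Exclusions for refractory shock and immediately life-threatening illness may keep early deaths few. The SAP's Per Protocol MITT set requires four initial doses. At six-hourly dosing these span 3 × 6 = 18 hours, so only about first-day deaths leave that set, and they stay in the SAP's ITT set.

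Three stronger readings are tempting and fail.

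- A reader might infer that the SAP contradicts itself, because this subject is unfavourable in Table 3 and not a failure here. These are separately named and defined endpoints, and different results under them are not a contradiction. A subject positive on every culture to Day 4 also fits persistence at least as well as presumed persistence.
- A reader might infer that every limb needs a culture late in follow-up. Limb 3 can be met within the first week.
- A reader might infer that the death certainly sits in the denominator as a non-failure, and so that a harmful drug would appear superior. The denominator is unstated. In the third assumed scenario the apparent 2-point advantage disappears if deaths are dropped.

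What remains is that the endpoint has its own proportions and between-arm p-value at three visits, and none of the neighbouring rules carries over to it.

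**Conclusion.** The point holds for this endpoint. A subject without documented clearance who dies before a qualifying culture cannot be a microbiological failure, and the plan has no rule that corrects this. Failure is understated in the arm with more such deaths, whichever denominator is used. The firm size is 4.0 points per death on active and 7.7 on placebo, assuming 25:13 and deaths kept as non-failures. The scenario differences and p-values above rest on assumed mortality and failure rates, treat every death as before clearance, and depend on the denominator. The documents do not support a claim that the trial as a whole hides early deaths. The defect is one misleading table, worth correcting because the correction is cheap.

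**What to change.** In SAP 2.3.2 and 3.4.1:

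- State that the denominator is all subjects in the analysis population.
- Count death before documented clearance (two consecutive negative days) as microbiological failure from the date of death onward, in line with the unfavourable Table 3 categories.
- Show deaths after clearance as a separate row at each visit.
- Keep the culture-only definition as a sensitivity analysis.
- List the change in SAP Section 6, since the protocol defines the endpoint by cultures alone.

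The cost is one derivation rule, using death and culture dates that other endpoints already need. Failure proportions will rise by the share of such deaths, and a few non-infectious deaths before clearance will be counted as failures. The sensitivity analysis shows how much of the result depends on them.
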